2.1 Trial design

A two-arm randomised feasibility study of SPECIFiC training course against waitlist controls. The control group will receive treatment as usual during the intervention period and will receive the parenting intervention after the intervention period (see appendix A of the protocol). Families will be randomised 1:1 into the intervention or control arm. The study will not affect any aspect of the participants' clinical care. The 7-week course will be delivered by trained facilitators, following the manual created in a prior study funded by the Medical Research Council (MRC). All materials and information are incorporated into this

SPECIFiC_SAP_V2.0 20th November 2024

manual. The intervention was set up to be delivered online to groups of 6 on a rolling basis. This will minimise wait times and allow for timely access to the intervention for the controls, who will be on a waitlist. All participants are to be eventually offered the intervention. The primary outcome measure for efficacy (Parenting Stress Index, PSI) will be used to compare the SPECIFIC arm against treatment as usual at 16 weeks. Following this, those on the control group will receive the intervention. See Appendix A (protocol) for the trial flowchart.

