2.7 Timing of outcome assessments

The timepoint for the proof-of-concept primary efficacy outcome assessment will be at 16 weeks, following the extended follow-up period. Note that the control group will have been receiving treatment as usual until the primary efficacy outcome assessment and the efficacy effect estimate will be the difference between intervention and no intervention. Data will

be collected from the control group 16 weeks after their intervention-baseline for future analyses but do not form part of this SAP.

Other questionnaire outcomes will also be assessed at 16 weeks. A secondary outcome is the comparison of the primary efficacy outcome at 8 weeks and 16 weeks, in the intervention group only. This outcome was added as part of a protocol amendment on 22 November 2023.

3 Statistical Principles

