3.3 Analysis populations

The primary analysis will be conducted following the intention-to-treat (ITT) principle, in accordance with the randomised intervention. All randomised families with baseline data and at least one follow-up timepoint will be included in the primary analysis, regardless of adherence to the protocol. Participants that withdraw from completing further follow-up data

collection but do not withdraw consent for the use of their data collected so far, will be included in the intention-to-treat analysis. Per-protocol analysis for the candidate primary outcome (PSI-4-SF) will be performed to analyse the difference between arms only in those parents and children where the family was deemed to be protocol compliant, defined as attending five or more of the seven session. Per-protocol analyses will not be carried out for secondary outcomes, i.e. an ITT analysis will be performed for all secondary outcomes.

4 Trial Population

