5.3.1 Primary outcome analysis

Primary analysis (ITT)

Candidate outcomes for the definitive trial including Parent stress (PSI-4-SF) will be compared between groups using a mixed model approach including all observed data at 16 weeks and adjusting for baseline measures and recruiting site. A binary variable will be included as fixed effect to indicate treatment allocation. Site, cohort, and baseline measure will be included as covariates; all control participants will be allocated a single cohort indicator. Inclusion of random subject effects will account for correlation between repeated outcomes on individual families. Estimated differences between groups and their 95% confidence intervals will be presented. The lower level of the 95% confidence interval for the difference between groups not ruling out an adjusted difference between groups of 7.3 points on the PSI-4-SF (as per the sample size calculation, section 3.4) will be considered sufficient to demonstrate proof-of-concept in the intervention. Subgroup analysis, such as whether outcomes differ according to time from diagnosis or age of index child will inform inclusion criteria and potential stratification factors for a larger trial. The PSI-4-SF outcome will also be available at 8 weeks in the intervention group only and will be reported; these data will not be included in the primary endpoint analysis. We will examine outcome profiles within the intervention group to see if any treatment effect is maximal during

training. These analyses are exploratory in nature and intended to help inform future research.

Per-protocol analysis

Sensitivity analyses will be conducted on the primary outcome to assess the robustness of results to failure to adhere to the protocol.

Per-protocol analysis for the candidate primary outcome (PSI-4-SF) will be performed to analyse the difference between arms in those parents and children where the family was deemed to be protocol compliant (see definition in Section 3.3). Per-protocol analyses will not be carried out for secondary outcomes.

Subgroup analyses

Subgroup analysis, such as whether outcomes differ according to time from diagnosis or by the age of the child will be done by adding the relevant factors to the mixed model as additional covariates and including an interaction term. The results from these analyses will inform inclusion criteria and potential stratification factors for a larger trial.

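### Per-protocol compliance is defined only by session attendance, which controls cannot meet before 16 weeks; the workable reading gives a non-randomised contrast open to selection bias

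*SAP*

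**What the plan says.** Section 3.3 makes ITT the primary analysis and adds a per-protocol analysis of PSI-4-SF "to analyse the difference between arms only in those parents and children where the family was deemed to be protocol compliant". The only criterion for compliance is session attendance; the set is limited to cases where "the family was deemed to be protocol compliant, defined as attending five or more of the seven session".

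Section 5.3.1 repeats the analysis, points back to Section 3.3 for the definition, and gives its purpose: "Sensitivity analyses will be conducted on the primary outcome to assess the robustness of results to failure to adhere to the protocol". It specifies no other sensitivity analysis of the primary efficacy outcome. Section 5.4 (Missing data) provides only for summarising missing data and exploring the reasons for them.

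On control exposure, Section 2.7 states: "Note that the control group will have been receiving treatment as usual until the primary efficacy outcome assessment". Section 2.1, after describing the 16-week comparison, adds: "Following this, those on the control group will receive the intervention".

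**The concern.** The compliance rule requires something that only one arm is offered before the outcome is measured. The SAP does not say how a control family enters the per-protocol set, so the analyst has to supply the rule. The current SAP version is dated 20 November 2024 and final data collection was 30 September 2024 (Section 2.6), so an analyst filling the gap would do so with the data already collected.

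The natural way to fill it also has a cost. Families who attended are compared with a control arm that still contains the families who would not have attended. If attendance is related to PSI-4-SF at 16 weeks after baseline adjustment, a difference appears even when the course has no effect. What is at stake is the plan's one check of the primary efficacy result against non-adherence.

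**Working it through.** **1. The plan's own figures.** Section 2.3 gives an effect size of 0.5, SD 14.62, target 7.3 points (0.5 × 14.62 = 7.31), one-sided 5% level and 80% power. The normal approximation gives 2 × (1.645 + 0.842)² / 0.5² = 49.5, so 50 per arm and 100 in total. The t-based calculation gives 51 per arm (power 0.806), 102 in total as stated. Allowing 10% attrition, 102 / 0.9 = 113.3, so 114, as stated. These figures are not in dispute; they supply 51 evaluable families per arm for what follows.

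**2. Who meets the rule by 16 weeks.**
- Literal reading, rule applied to both arms: 0 of 51 controls qualify, so there is no between-arm difference to estimate. This holds even if every intervention family attends.
- Rule applied to the intervention arm only: all 51 controls are compared with about 46, 41 or 36 attenders at assumed compliance of 90%, 80% or 70%.
- Controls classified by attendance at their later course: the SAP does not say this, and it would select controls on behaviour after their 16-week outcome.

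**3. Bias in the intervention-only reading.** Let q be the share of intervention families dropped and g the mean adjusted PSI-4-SF of dropped minus retained families. With no treatment effect, the whole intervention arm has the control mean, and the retained families lie q × g below it. So bias = q × g, and a positive value looks like benefit. If dropped families score lower, g is negative and the bias runs against SPECIFiC. The SAP gives neither q nor g; the values below are assumptions, shown for positive g.

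| q | g (points) | bias (points) | share of 7.3 |
|---|---|---|---|
| 0 | any | 0 | 0% |
| 10% | 5 | 0.5 | 7% |
| 20% | 5 | 1.0 | 14% |
| 20% | 10 | 2.0 | 27% |
| 30% | 10 | 3.0 | 41% |

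A 10-point gap after baseline adjustment is a strong assumption: 10 / 14.62 = 0.68 SD.

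**4. Cross-check with another model.** If attendance is selection on a normal variable whose correlation with the outcome has size ρ, the bias has size ρ × SD × φ(z) / p. Here p is the compliance proportion, z is the normal quantile at 1 − p, φ is the normal density and SD is 14.62. For an assumed ρ of 0.1 to 0.5, the bias is 0.29 to 1.43 points at p = 90%, 0.51 to 2.56 at 80%, and 0.73 to 3.63 at 70%. The two approaches give the same order of magnitude.

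**5. The only attendance data in the plan.** Section 2.3 reports nine test-run families: eight attended everything and one missed two sessions. If that run had seven sessions, attendance was 61/63 = 97%, which matches the stated figure. The ninth family attended five sessions, so all nine would have met the rule and q would have been 0.

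**The case against.** The strongest reply is that the literal reading is not what was meant. Both sections ask for a difference between arms, which presupposes a control arm, and an attendance rule applies naturally to the arm that is offered sessions. An analyst would probably keep all controls. That is fair: a reader might infer that the analysis cannot be run at all, and the text does not support going that far. What stands is that the rule for controls is missing and that the likely reading is a selected comparison.

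The second reply is that loss of randomisation is common to per-protocol analyses and that the plan contains it. ITT is primary, the 7.3-point proof-of-concept rule sits under the ITT heading in Section 5.3.1, the progression criteria in Section 5.1.2 do not mention per-protocol results, and Section 2.4 says the trial does not seek to show superiority. This also stands, and it limits the severity.

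Third, a reader might infer that the bias favours SPECIFiC because the most stressed families miss most sessions. The SAP offers no evidence for that. The one recorded reason for absence is work commitments, and baseline PSI-4-SF is a covariate. Exclusions may also be few, since Section 4.2.1 requires parents to be able to commit to all seven sessions. Nine test-run families, however, cannot rule out appreciable non-attendance.

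Finally, an instrumental-variable analysis brings its own assumption, which is addressed under the fix.

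**Conclusion.** The point holds as a modest defect. Followed literally, the attendance rule leaves no controls. Followed sensibly, it gives a contrast that randomisation does not protect. The size of the bias is unknown: near zero if almost all families attend, 0.5 points at 10% dropped and a 5-point gap, and 3 points (41% of the 7.3-point target) at 30% and 10 points. All non-zero figures rest on assumed values of both inputs, and the direction is not established. The defect does not touch the ITT result or any stated progression decision. It matters because this is the only sensitivity analysis specified for the primary efficacy outcome, and a better one is available from data already being reported.

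**What to change.** For the non-adherence sensitivity analysis, specify a complier average causal effect. Use two-stage least squares with randomised arm as the instrument for attending at least five sessions, adjusted for baseline PSI-4-SF and site, in all randomised families with a 16-week PSI-4-SF. Controls have no access before 16 weeks by design, so the estimate is close to the ITT difference divided by the compliance proportion p. For illustration, an ITT difference of 5 points at 80% compliance gives 5 / 0.8 = 6.25.

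State the exclusion restriction: attending one to four sessions is taken to have no effect. If those sessions help, the estimate is too large, by (1 − p)/p times the mean effect in families below five sessions (0.2 / 0.8, a quarter of that effect, at 80%). Repeat the analysis with number of sessions attended as the exposure, which avoids the cut-off but assumes that each session adds the same amount.

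If a per-protocol contrast is also kept, state that the attendance criterion applies to the intervention arm only, that all controls with 16-week data are retained, and that the result is a non-randomised, supportive comparison.

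The cost is SAP wording and a short piece of code. No new data are needed, because Section 3.2 already reports sessions attended. The downsides are the exclusion assumption and a wider interval: about 1/p times the ITT width, or 1.25 times at 80% compliance.

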4.1 Screening, recruitment, withdrawal/follow-up

Families screened but not enrolled in the trial and reasons for exclusions will be reported; recruitment will be presented by site. The period of data collection, including the date of the first randomisation and first parenting course, and date of the final follow up visits will be described.

The number of families who have withdrawn or were unwilling to continue follow-up will be reported by treatment arm.

The throughput of families from those screened to those who are enrolled and assessed for trial endpoints, and included in the analysis, will be summarised in a CONSORT flowchart.

4.2 Eligibility

4.2.1 Inclusion Criteria

Index child inclusion criteria:

- Age 4-16 years (school years R to 11)

- Diagnosis in line with internationally agreed criteria for FASD (or if a medical professional has stated that the index child probably has FASD – these cases were screened by our clinical partner [name])
- Diagnosed within previous five years

Parent inclusion criteria

- Able to commit to all seven sessions
- Willing to wait for the intervention if required
- Lives with and is the legal guardian of the index child

4.2.2 Exclusion Criteria

- Parent exclusion criteria
- Ever previously undergone specialist parenting training for FASD
- Severe depression (identified at the eligibility assessment screening (DASS-21))
- Presence of acute safeguarding issues or concerns (including current harmful use of alcohol (identified at the eligibility assessment screening (AUDIT)))

See protocol section 8.3 for further detail.

4.3 Baseline patient characteristics

The following baseline characteristics will be summarised by randomised group with mean (standard deviation) or median (interquartile range) for continuous variables, and frequency (percentage) for categorical variables.

- Parent characteristics
 - Age at consent
 - Gender
 - Country
 - Education

- Household income
- Family characteristics (how many children, how many children with FASD diagnosis)
- Relationship to child
- Child demographics
 - Age at consent
 - Gender
 - Ethnicity
 - FASD diagnosis

5 Analysis

5.1 Outcomes

5.1.1 Primary outcomes for this feasibility study:

- Percentage of eligible parents invited who agree to participate.
- Percentage of those participating who complete the study.
- Primary efficacy outcome (proof-of-concept): **Parent stress** post-intervention extended follow-up (16 weeks - Time 3) using the *Parenting Stress Index 4th edition Short Form (PSI-4-SF)* total score.

5.1.2 Pre-specified criteria for progression to a definitive RCT

The assessment for the next phase would consider progression criteria using a traffic light system if the Trial Steering Committee are satisfied that the following feasibility criteria are met (or can be reasonably mitigated with changes to the suggested protocol):

- *Recruitment: 0-25% = red; 26-50% = amber; 51-100% = green*
 - *Percentage of eligible parents invited who agree to participate.*
- *Retention: 0-50% = red; 50-70% = amber; 71-100% = green*

- *Percentage of those participating who complete the study.*
- *Satisfaction: 0-50%=red; 51-70%=amber; 71-100% =green*
 - *Percentage of those who express satisfaction with the session, as captured by the SPECIFiC session evaluation form.*
- *Estimated differences in primary outcome (PSI-4-SF total score) at 16 weeks: does not favour SPECIFiC=red; does not favour either SPECIFiC or TAU=amber; favours SPECIFiC = green.*

If red/amber results are obtained, the qualitative evaluation will be used to potentially remedy problems. Where it is deemed that identified problems cannot be managed, an RCT will not go ahead.

5.1.3 Secondary outcomes included in the SAP:

- MCID PSI-4-SF:
 - Estimate the difference in PSI-4-SF scores at 16 weeks with sufficient precision to inform a wider discussion around the clinical efficacy of the intervention and how the PSI-4-SF performs as a primary efficacy outcome for a future RCT.
- Data completeness:
 - Levels of missing data for the proof-of-concept primary efficacy outcome by timepoint
- Parent stress:
 - *(PSI-4-SF)* at Time 2 (8 weeks): to compare with the primary outcome (Time 3 PSI-4-SF) to determine whether intervention effects change over time. Note this outcome is only measured in the intervention group, due to the trial design (waitlist controls).
- Children's behavioural difficulties:
 - The Strengths and Difficulties Questionnaire (SDQ)
 - The Eyberg Child Behaviour Inventory (ECBI)

- Parents' psychological wellbeing:
 - *The Clinical Outcomes in Routine Evaluation–Outcome Measure (CORE-OM)*
- Parental mental health scale:
 - Depression Anxiety Stress Scales (DASS-21).
- Parenting self-efficacy:
 - Tool to measure Parenting Self-Efficacy (TOPSE)
- Group sizes

5.1.4 Other outcomes (not within scope of the SAP)

- Acceptability (qualitative)
- Fidelity to training manual (qualitative)
- Performance of the research instruments and outcome measures (including economic outcomes instruments and measures)

5.2 Outcome definitions

All validated questionnaires will be scored according to the appropriate scoring manual, unless stated otherwise.

- **Parent stress** post-intervention extended follow-up (16 weeks) using the *Parenting Stress Index 4th edition Short Form (PSI-4-SF)*. This is a 36-item respondent-based rating scale, selected as a valid and reliable measure of internal stress and dynamics within a family system. It is highly cited, reliable instrument which has been used in similar studies. This is chosen as the candidate primary outcome at Time 3 (16-week extended follow-up) because the theoretical basis of the intervention assumes that there will be reduction in parent stress in the medium term.
- **Children's behavioural difficulties:** The Strengths and Difficulties Questionnaire (SDQ) and the Eyberg Child Behaviour Inventory (ECBI); are parent-reported measures, both well-established for measuring behavioural difficulties in children.

- **Parents' psychological wellbeing:** *The Clinical Outcomes in Routine Evaluation– Outcome Measure (CORE-OM)*, which measures change following psychological interventions. It covers subjective wellbeing, anxiety and depression, physical symptoms, effects of trauma, social isolation, life satisfaction, and risks to oneself and others.
- **Progression criteria – satisfaction:** Parents were asked to complete the SPECIFIC session evaluation form after each session of SPECIFIC, with 16 questions. Question 1 refers to the facilitators and is not included in the scoring. Questions 2 to 16 have five possible responses; Strongly disagree, Disagree, Neutral, Agree, Strongly agree, mapping to scores of 0 to 4 respectively. These will be summed, giving a total satisfaction score ranging from 0 to 60, with 60 indicating total satisfaction with that session. For each participant, their total scores from each of the seven sessions (or every session attended) will be averaged, giving each participant a single score ranging from 0 to 60. These scores will then be averaged across all participants and expressed as a percentage to which the progression criteria cut-offs can be applied.
- **EQ-5D-5L** was chosen as the preferred measure of health-related quality of life for intervention studies and its use will inform the health economics assessment in the feasibility trial and full randomized controlled trial.
- The **CORE-OM** was chosen as a measure of change following psychological interventions, and the **FASD Knowledge Questionnaire** was designed especially for this study as a measure of knowledge improvement.
- **The Tool to Measure Parenting Self-Efficacy (TOPSE)** is a 48-item caregiver-report questionnaire designed to assess the impact of parent-related interventions on caregivers' sense of their own parenting self-efficacy.

Further details of questionnaires including references can be found in the Appendix attached to this SAP, or in the protocol.

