5.3 Analysis methods

Statistical analysis will be mainly descriptive and focus on establishing the recruitment and retention rates that would indicate a trial is feasible, and to estimate parameters which will inform the sample size for the main trial. Recruitment, retention, and satisfaction rates will be presented by group with 95% exact confidence intervals.

Observed data from all randomised participants will be included in the analysis following the intention-to-treat principle.

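### The satisfaction criterion is defined as a percentage of satisfied parents but computed as a mean score, and the same red/amber/green cut-offs can colour the two differently

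*SAP*

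**What the plan says.** Three sections of the SAP deal with satisfaction.

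- **Section 5.1.2** (progression criteria) describes the quantity as "Percentage of those who express satisfaction with the session, as captured by the SPECIFiC session evaluation form" and attaches the bands "Satisfaction: 0-50%=red; 51-70%=amber; 71-100% =green".
- **Section 5.2** (outcome definitions) gives the scoring. The form has 16 questions, and "Question 1 refers to the facilitators and is not included in the scoring". For the rest, "Questions 2 to 16 have five possible responses; Strongly disagree, Disagree, Neutral, Agree, Strongly agree, mapping to scores of 0 to 4 respectively". The items are summed, "giving a total satisfaction score ranging from 0 to 60, with 60 indicating total satisfaction with that session". Session totals are then "averaged, giving each participant a single score ranging from 0 to 60". Last comes the step to the bands: "These scores will then be averaged across all participants and expressed as a percentage to which the progression criteria cut-offs can be applied".
- **Section 5.3** (analysis methods) says "Recruitment, retention, and satisfaction rates will be presented by group with 95% exact confidence intervals".

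No section gives a score at which a parent counts as satisfied. The dummy Table 2c in section 6.1 has one result and one rating for satisfaction.

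**The concern.** Section 5.1.2 counts people; section 5.2 averages scores. A percentage of people and a mean expressed as a percentage of its maximum share a 0-100 range but measure different things, so one set of cut-offs need not grade them alike. Section 5.3 follows the first definition, since the usual exact interval is for a binomial count.

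At stake is the colour given to the Trial Steering Committee for one of four progression criteria. Section 5.1.2 provides that a definitive trial will not go ahead if problems are found that cannot be managed. With a single line in Table 2c, the committee would not see which quantity had been graded.

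**Working it through.** **Inputs.** 16 questions with the first excluded, item scores 0 to 4, range 0 to 60 (section 5.2); bands red 0-50, amber 51-70, green 71-100 (section 5.1.2); target of 120 families allocated 1:1 (section 2.3).

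**Assumptions.** The SAP does not name the divisor for the percentage; 60 is the natural reading. For illustration, each parent gives the same answer to every item at every session, and a parent is satisfied if that answer is Agree or Strongly agree.

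**Step 1: the SAP's own figure.** (16 − 1) items × 4 = 60. The stated maximum reproduces.

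**Step 2: what the percentage means.** Percentage = 100 × (15 × item score) / 60.

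- Strongly disagree: 0/60 = 0%
- Disagree: 15/60 = 25%
- Neutral: 30/60 = 50%
- Agree: 45/60 = 75%
- Strongly agree: 60/60 = 100%

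If everyone is Neutral, the mean measure is 50% while nobody has expressed satisfaction. If everyone agrees, it is 75% while all have. Green starts at 0.71 × 60 = 42.6, or 42.6/15 = 2.84 per item, a little below Agree.

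**Step 3: the two quantities in hypothetical mixes.** Mean measure = 100 × Σ(share × score) / 60.

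| Mix of parents | Mean score | Section 5.2 measure | Section 5.1.2 measure |
|---|---|---|---|
| 80% Agree, 20% Neutral | 36 + 6 = 42 | 70.0%, amber | 80%, green |
| 75% Agree, 25% Neutral | 33.75 + 7.5 = 41.25 | 68.75%, amber | 75%, green |
| 80% Agree, 20% Disagree | 36 + 3 = 39 | 65%, amber | 80%, green |
| 50% Strongly agree, 50% Neutral | 30 + 15 = 45 | 75%, green | 50%, red |
| 45% Strongly agree, 55% Neutral | 27 + 16.5 = 43.5 | 72.5%, green | 45%, red |
| 20% Agree, 80% Neutral | 9 + 24 = 33 | 55%, amber | 20%, red |
| 60% Agree, 40% Neutral | 27 + 12 = 39 | 65%, amber | 60%, amber |

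**Step 4: share satisfied when the mean measure reaches 71%.**

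- Neutral/Agree group: (0.71 − 0.50) / (0.75 − 0.50) = 0.84, so 84% must be satisfied.
- Neutral/Strongly agree group: (0.71 − 0.50) / (1.00 − 0.50) = 0.42, so 42% is enough.

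**Step 5: the interval.** The Clopper-Pearson interval needs a count out of a total. With 60 parents (120/2, all supplying forms, an assumption), 48 satisfied gives 67.7% to 89.2% and 30 satisfied gives 36.8% to 63.2%. Section 5.2 produces no such count.

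**The case against.** **Section 5.2 may be the intended rule.** It is the explicit, reproducible scoring rule and is labelled as the progression criterion, whereas section 5.1.2 gives no threshold for a satisfied parent. The bands can also be read on the mean scale: all Neutral falls at the top of red and all Agree falls in green. No derivation of the cut-offs is shown. This stands. It means the documents do not settle which rule governs; it does not remove the conflict.

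**The mixes are invented.** The SAP contains no satisfaction data, some mixes give the same colour under both rules, and the 80/20 mix lands exactly on the amber ceiling. This stands in part: the examples show that a discrepancy is possible, not that it is likely. The 75/25 and 50/50 mixes do not depend on the amber ceiling.

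**The interval is a matter of wording.** The sentence in section 5.3 also covers recruitment and retention, for which an exact interval is right, and a mean score could have an ordinary interval for a mean. This stands; it would be too strong to say that no interval can be given.

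**The consequence is limited.** Satisfaction is not listed as a primary outcome in section 5.1.1. Section 5.1.2 lets the committee accept mitigation and refers red and amber results to the qualitative evaluation. The efficacy estimate is unaffected. This lowers the severity.

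**Two further inferences are not supported.** A reader might infer that averaging over attended sessions leaves out families who stopped coming. It does not: a parent who attended two sessions still contributes one equally weighted score, and only parents with no form drop out. A reader might also infer that reporting by group is impossible because controls have no course before 16 weeks. Section 5.2 does not limit the forms to one arm, and controls take the course later (section 2.1). Section 2.7 puts control data collected 16 weeks after their intervention baseline outside this SAP but does not mention session forms. This is an ambiguity, not an error.

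**Conclusion.** The inconsistency is real and should be fixed, though it does not threaten the trial's main estimates. Sections 5.1.2 and 5.2 apply one set of cut-offs to two different quantities, and the interval in section 5.3 fits only the first. The colour can differ by one step in the harsh direction (green to amber) or by two in the lenient direction (red to green).

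It is tempting to say that section 5.2 gives the wrong colour. That holds only relative to section 5.1.2, and the SAP does not say which section prevails. The sizes rest on division by 60, uniform answers within each parent, and Agree or better counting as satisfied. None of these is stated in the SAP.

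**What to change.** State one rule, in the same terms in sections 5.1.2, 5.2 and 5.3, and document it before the satisfaction result is seen.

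- **Preferred:** keep the section 5.1.2 criterion and the exact interval. Classify each parent with at least one form as satisfied or not by a stated threshold, for example a mean session score of at least 45/60 (average Agree). Apply the cut-offs to the percentage satisfied, with a Clopper-Pearson 95% interval, and report the mean score descriptively.
- **Alternative:** redefine section 5.1.2 as a mean percentage score, name 60 as the divisor, justify the cut-offs on that scale, and replace the exact interval for satisfaction with one for a mean.

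Under either option, state which arm's session forms are used. Counting parents who stopped attending as dissatisfied is not advised, because it would mix satisfaction with retention, which is a separate criterion.

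The cost is SAP wording and a small change to the analysis, using forms already collected. The rating may become more or less favourable. The 45/60 threshold appears nowhere in the SAP. Final data collection was 30 September 2024 (section 2.6) and this SAP version is dated 20 November 2024, so any threshold must be labelled as set after data collection.
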